8. RESEARCH QUESTION AND OBJECTIVES

This study aims to assess real-world effectiveness in HR+/HER2- MBC patients initiating palbociclib + AI or AI alone as first-line therapy during the period 01 February2015 through March 2020.

Primary Objective

• To compare overall survival (OS) of first line palbociclib + AI versus AI alone for postmenopausal women or men with HR+/HER2- MBC

Secondary objectives

- To compare real-world progression free survival (rwPFS) and real-world tumor response (rwTR) of first line palbociclib + AI versus AI alone for postmenopausal women or men with HR+/HER2- MBC
- To describe treatment patterns of Palbociclib, including initial dose, dose adjustment, treatment duration, subsequent treatments, and time to chemotherapy

9. RESEARCH METHODS

9.1. Study design

The primary objective of the retrospective EHR database analysis is to compare effectiveness outcomes of palbociclib + AI versus AI alone as first line MBC treatment for HR+/HER2-MBC postmenopausal women or men.

The following table lists 7 key components of the study protocol.

D 4 10	D '.'
Protocol Component	Description
Eligibility criteria	All patients with HR+/HER2- MBC who were initiated with palbociclib + AI or AI alone as 1 st line therapy for their MBC during the period of February 2015 through March 2020 were registered in the Flatiron Health Analytic Database
Treatment regimen	Palbociclib + AI or AI alone as the first line MBC treatment
Study cohorts	Patients will be divided into either Palbociclib + AI or AI alone cohort according to their first line MBC treatment received
Follow-up period	From index date (i.e., starting date of the first line MBC treatment during the period of 03 February 2015 through March 2020) to death or study end (date of data cutoff, September 30, 2021), whichever occurred first
Primary outcome	Overall survival (OS)
Causal contrasts of interest	Intention-to-treat effect
Analysis plan	Intention-to-treat effect requires adjustments for baseline prognostic factors using IPTW approach. In addition, to address unmeasured confounding, sensitivity analyses will also be performed to determine the robustness of the estimated intention-to-treat effects.

9.2. Setting

This study uses secondary de-identified Flatiron Healthcare Analytic data that involve patients who have been diagnosed with MBC in the United States.

9.2.1. Inclusion criteria

Patients must meet all the following inclusion criteria to be eligible for the study:

- 1. At least 18 years old at MBC diagnosis
- 2. Diagnosis of MBC at any point in patient history
 - a. ICD-9 (174.x, 175.x) or ICD-10 (C50.xx) diagnosis of BC
 - b. At least 2 documented clinical visits on or after 01 January 2011
 - c. Evidence of stage IV or recurrent MBC with a metastatic diagnosis date on or after 2011, as confirmed by unstructured clinical documents
- 3. Confirmed HR+/HER2- status as defined as
 - a. HR+: ER+ or PR+ test before or up to 60 days after MBC diagnosis
 - b. HER2-: any HER2 negative test and the absence of a positive test (IHC positive 3+, FISH positive/amplified, positive NOS) before or up to 60 days after MBC diagnosis
- 4. Received Palbociclib + AI or AI as first line treatment for MBC during the period from 03 February 2015 through March 2020
- 5. A potential minimum follow-up of 6 months from index treatment until the data cutoff date, September 30, 2020:

9.2.2. Exclusion criteria

Patients meeting any of the following criteria will not be included in the study:

- 1. Evidence of any prior treatments with CDK 4/6 inhibitors (i.e., palbociclib, ribociclib or abemaciclib), endocrine treatments (e.g., tamoxifen, raloxifene, toremifene, or fulvestrant), or chemotherapy in the MBC setting
- 2. First structured activity greater than 90 days after MBC diagnostic date
- 3. Lacks relevant unstructured documents in the Flatiron Health database for review by the abstraction team

9.3. Variables

All variables are assessed or defined by Flatiron using business rules before and after Palbociclib + AI or AI alone initiation.

Variable	Operational definition
Demographic characteristics	
Age	Age at MBC diagnosis, years
Age category	<50, 50-64, 65 –74, ≥75 years
Index treatment year	2015, 2016, 2017, 2018, 2019, 2020
Gender	Male, female, unknown
Race	White, Black, Asian, other, unknown
Region of residence	Based on region where the patient resides: Northeast, Midwest,
	South, West
Practice type	Academic, community
Insurance type	Commercial, Medicare, Medicaid

Palbociclib (IBRANCE®) A5481151, NON-INTERVENTIONAL STUDY PROTOCOL Protocol Amendment 1, 16 Feb 2022

Management at the			
Menopause status	Pre or perimenopausal, postmenopausal, Unknown as defined by Flatiron.		
	Menopausal status was either assigned or abstracted,		
	depending on the patient's age at 1L start. The following		
	was used to determine menopausal status:		
	Patients age 60 years or older at 1L start date are		
	assigned as "postmenopausal".		
	• Patients younger than age 60 at 1L start underwent		
	abstraction for menopausal status and are categorized as		
	follows:		
	o If there was explicit documentation by the		
	clinician of the patient being "postmenopausal" or		
	patient was stated as being menopausal at a certain		
	age prior to the start of first-line therapy for		
	metastatic breast cancer, or implicit documentation		
	of "Prior Bilateral Salpingo-Oophorectomy (BSO)		
	with or without hysterectomy" prior to or within 30		
	days after the 1L start, the patient's menopausal		
	status was derived as "postmenopausal"		
	 If there was explicit documentation by the 		
	clinician of the patient being "premenopausal" or		
	implicit documentation of "Regular menses",		
	between the metastatic breast cancer diagnosis date		
	and up to 30 days following the start of first-line		
	therapy the patient's menopausal status was derived		
	as "premenopausal"		
	If there was explicit documentation by the		
	clinician of the patient being "perimenopausal"		
	between the metastatic breast cancer diagnosis date		
	and up to 30 days following the start of first-line		
	therapy the patient's menopausal status was derived		
	as perimenopausal		
	If there is no explicit or implicit documentation		
	of menopausal status prior to or within 30 days		
	1 1		
	after the 1L start, the patients were considered as		
	having "Unknown" menopausal status		

Time to 1st subsequent chemotherapy	Months from the start of palbociclib plus AI or AI alone to next line of anticancer therapy/chemotherapy, death form any cause, last visit, or end of study, whichever came first
Effectiveness outcomes	
Real-world PFS (rwPFS)	Real-world PFS is defined as the number of months from start of palbociclib + AI or AI alone to death from any cause or disease progression (based on clinical assessment or by radiographic

Protocol Amendment 1, 16 Feb 20	scan/tissue biopsy), whichever occurred first. Patients who did not die and did not have disease progression will be censored at the date of initiation of next line of therapy for patients with 2 or more lines of therapy or at the date of their last visit during the study period (February 2015- September 2020) for patients with only 1 line of therapy.
rwPFS2	rwPFS2 is defined as the number of months from start of palbociclib + AI or AI alone to disease progression (based on clinical assessment or by radiographic scan/tissue biopsy) on the 2 nd line of therapy or death from any cause, whichever occurred first. Patients who did not die and did not have disease progression on the 2nd line of therapy will be censored at the date of initiation of 3 rd line of therapy for patients with 3 or more lines of therapy or at the date of their last visit during the study period (February 2015- September 2020) for patients with only 1 or 2 lines of therapy ²⁹ .
Overall survival (OS)	Overall survival (OS) was defined as the number of months from start of palbociclib + AI or AI alone to death. Patients who did not die, will be censored at the end of study date. Date of death. In most Flatiron deliverables, death data is delivered with a month granularity. Date of death is a consensus variable across the three data sources (EHR, SSDI and obituary data). Flatiron generates the variable according to the following rules and hierarchy (preference is based on comparative analyses with the National Death Index as the gold standard): Use abstracted dates over structured dates when the abstracted date granularity is at the day level. Use the following rules when there are multiple structured dates of death: If all three dates are in agreement, that date of death is selected If any two dates are in agreement, that date of death is selected If none of the dates are in agreement, then the rank order to which the date of death is selected is: SSDI→Obituary data→EHR
Real-world tumor responses (rwTR)	Real-world best responses are assessed based on treating clinician's assessment of radiological evidence for change in burden of disease over the course of treatment after 1 month of index treatment initiation. Complete response: complete resolution of all visible disease. Partial response: partial reduction in size of visible disease in some or all areas without any areas of increase in visible disease.

Stable disease: no change in overall size of visible disease; also included cases where some lesions increased in size and some lesions decreased in size
Progressive disease: an increase in visible disease and/or
presence of any new lesions; included cases where the
clinician indicated progressive disease

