Overall survival is defined as the number of months from start of palbociclib + AI or AI alone to death. Patients who did not die will be censored at the date of last follow-up or date of data cutoff during the study period from February 2015- September 2020. Real-world PFS (rwPFS) will be defined as the number of months from start of palbociclib + AI or AI alone to death or disease progression (based on clinical assessment or by radiographic scan/tissue biopsy per Flatiron rules), whichever occurred first. Patients who did not die or did not have disease progression, will be censored at the date of initiation of next line of therapy for patients with 2 or more lines of therapy or the date of their last visit during the study period (February 2015- September 2020) for patients who only received 1 line of therapy. Real-world tumor responses (rwTR) are assessed based on treating clinician's assessment of radiological evidence for change in burden of disease over the course of treatment.

The comparative analyses for the study objectives of assessing effectiveness outcomes of palbociclib + AI versus AI alone will be conducted applying inverse probability treatment

weighting (IPTW) to balance baseline demographic and clinical characteristics between the comparison cohorts.

Population Setting: This study uses secondary de-identified Flatiron Healthcare Analytic data that involve men and women who have been diagnosed with MBC in the United States.

Study Population: Patients who were 18 years of age or older at MBC diagnosis, had HR+/HER2- confirmed and initiated palbociclib + AI or AI alone as first line therapy in the metastatic setting during the period from February 2015 through March 2020 will be included in the analyses. Eligible patients will be identified from the Flatiron Health Analytic Database.

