9.4.2. Overall Survival for Real-world patients

A key goal of evidence-based medicine is to identify survival benefit associated with a treatment regimen, and therefore, considerable effort is dedicated to collecting mortality information in clinical trials to enable outcomes analyses, one of which is overall survival. With respect to the primary endpoint OS, Flatiron curates mortality information from 3

sources. These include EHR capture of patient's date of death as entered a structured field in the EHR or information captured in unstructured documents such as clinician notes and condolence letters. Additionally, the EHR data is linked with external death data sources to add in dates of death that might be missing from the EHR. In order to determine the optimal external death data source(s), options are evaluated on the basis of completeness, accuracy, and recency. Based upon this review, Flatiron selected to combine 2 external sources: the SSDI, and a commercial death dataset that mines data from obituaries, funeral homes, and other sources to provide death data that is current within a week of the death. A deterministic matching algorithm is employed to link these external datasets to patient-level data. Dates known to be incorrect (for instance, death dates that occur before abstracted diagnosis dates), as well as those required to be removed for de-identification reasons, specifically when a date of death occurs in the same month as the patient's advanced or metastatic diagnosis date are removed. Date of death is a consensus variable across the 3 data sources (EHR, SSDI and commercial death dataset)^{30, 31}. The variable is generated according to the following rules and hierarchy (preference is based on comparative analyses with the National Death Index as the gold standard):

- 1. Use abstracted dates over structured dates when the abstracted date granularity is at the day level.
- 2. Use the following rules when there are multiple structured dates of death:
 - 1. Social Security Death Index
 - 2. Commercial death dataset
 - 3. EHR
 - 4. If all 3 dates are in agreement, that date of death is selected
 - 5. If any 2 dates are in agreement, that date of death is selected
 - 6. If none of the dates are in agreement, then there is a rank order to which the date of death is selected: SSDI, Obituary data, and EHR

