Flatiron Health's publication in Health Services Research, "Development and Validation of a High-Quality Composite Real-World Mortality Endpoint," describes how Flatiron Health's mortality variable is benchmarked through comparisons with the National Death Index (NDI)³¹, which is widely considered a gold standard death dataset in the United States (. This publication concluded that Flatiron Health's mortality data has high sensitivity (85-90%), specificity (97-98%) and date accuracy (95-97%) varying across 4 different tumor types, (i.e. advanced non-small-cell lung cancer, advanced melanoma, metastatic colorectal cancer, and metastatic breast cancer). Recent analysis confirmed the validity of the approach to identify mortality³⁰.

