9.7.4.3. Analyses of secondary CC

Real-world progression-free survival (rwPFS) is defined as the time from index date to the date of the first documentation of a rwPD or death due to any cause, whichever occurs first. Patients last known to be alive and progression-free within the follow up cut-off date are censored at the date of the last clinic note. rwPFS2 is defined as the time from the index date to the date of the first documentation of a rwPD or death due to any cause after starting 2nd line of therapy, whichever occurs first.

rwPFS and rwPFS2 will be summarized using the weighted Kaplan-Meier method and displayed graphically where appropriate. The median rwPFS/PFS2 time will be estimated and corresponding 2-sided 95% CI for the median using the Brookmeyer-Crowley method.

rwPFS rates at 6, 12, 18, 24, 30, and 36 months will be estimated with corresponding 2-sided 95% CIs using the weighted Kaplan-Meier method. The weighted Cox Proportional hazards model will be fitted to compute the hazard ratio and the corresponding 95% CI.

Real-world tumor responses (rwTR) are assessed based on treating clinician's assessment of radiological evidence for change in burden of disease over the course of treatment after 30 days of index treatment initiation.

- Complete response: complete resolution of all visible disease.
- Partial response: partial reduction in size of visible disease in some or all areas without any areas of increase in visible disease.
- Stable disease: no change in overall size of visible disease; also included cases where some lesions increased in size and some lesions decreased in size
- Progressive disease: an increase in visible disease and/or presence of any new lesions; included cases where the clinician indicated progressive disease.

Real-world tumor response rate (rwTR) is defined as the proportion of patients with a real-world complete response (rwCR) or real-world partial response (rwPR). Patients who have inadequate data for tumor assessment (e.g. no baseline assessment or no post-baseline follow-up assessments), who receive anticancer medication other than the study medication prior to reaching a rwCR or rwPR, or who die, progress, or drop out for any reason prior to reaching a rwCR or rwPR will be counted as non-responders in the rwTR analysis.

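### As written, rwPFS and rwPFS2 stop the clock at next line or last visit only for patients with no later event, so censoring depends on the future outcome

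*Protocol*

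**What the plan says.** Protocol 9.3 (Variables) defines rwPFS as time from "start of palbociclib + AI or AI alone to death from any cause or disease progression", whichever comes first. Neither event is tied to first line. Censoring is then stated for one group only: "Patients who did not die and did not have disease progression will be censored at the date of initiation of next line of therapy" if they had two or more lines, or else "at the date of their last visit during the study period (February 2015- September 2020) for patients with only 1 line of therapy". SAP 5.1 repeats this. For rwPFS2, both documents use the same form with third-line start as the boundary, again only for patients who did not die and did not progress on second line.

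Two other places give different rules for rwPFS:

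- Protocol 9.7.4.3: "Patients last known to be alive and progression-free within the follow up cut-off date are censored at the date of the last clinic note". There is no next-line rule.
- Protocol Abstract: "Patients who did not die or did not have disease progression, will be censored at the date of initiation of next line of therapy". It has *or* where 9.3 has *and*. Read literally, it would censor a patient who died without progression.

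On deaths, Protocol 9.4.2 says that "the EHR data is linked with external death data sources to add in dates of death that might be missing from the EHR". No comparable outside source is described for progression.

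**The concern.** Kaplan-Meier and Cox methods need the end of a patient's observation to be fixed without reference to what happens afterwards. Here it is not. Take three patients who all start second line at month 8 with no documented progression:

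- One is alive with no recorded progression at cutoff: censored at month 8.
- One dies at month 40: first-line rwPFS event at month 40.
- One progresses on second line: on the literal text, a first-line event on that date.

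Time after month 8 enters the risk set only for patients who go on to have an event. The same happens after the last visit, for deaths alone, because linkage can still find them.

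The arms need not be affected equally. Under the line-of-therapy rule in 9.3, adding a CDK4/6 inhibitor to an AI beyond the 60-day threshold advances the line. That produces next-line starts, possibly without progression, specifically under AI alone. Index year is collected but is not among the propensity-score covariates in SAP 5.2, so arm differences in potential follow-up are not directly weighted away. The rwPFS medians, landmark rates and HR are at stake.

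**Working it through.** **Step 1: the four texts side by side.**

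| Place | Who is censored | When | Limit on later death or progression |
|---|---|---|---|
| Abstract | did not die *or* did not progress | next line / last visit | none |
| Protocol 9.3 | did not die *and* did not progress | next line / last visit | none |
| Protocol 9.7.4.3 | last known alive and progression-free | last clinic note | none |
| SAP 5.1 | as 9.3 | as 9.3 | none |

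The 9.7.4.3 rule would remove the next-line problem but leaves deaths after last contact. For rwPFS2, 9.3 limits progression to second line, so only later deaths are at issue. The sensitivity analyses in Protocol 9.7.4.4 are for the primary endpoint. SAP 7.2 covers matching, the line-of-therapy window and missing tumor response.

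**Step 2: inputs for size.** The plan gives no rwPFS event count or power, so there is no figure to reproduce.

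- From the documents: earlier-study rwPFS medians 20.0 and 11.9 months; index dates 03 February 2015 to 31 March 2020 and cutoff 30 September 2020, so follow-up runs from 6 to 67.9 months; death-capture sensitivity 85-90% (88% used).
- Assumed: next line without progression 0.5-4% per month; loss of visits 0.5% per month; death hazard 0.004 per month before progression and 0.027 after.

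With exponential times, the event hazard is ln 2 / median: 0.6931/11.9 = 0.0582 and 0.6931/20.0 = 0.0347. The true HR is 11.9/20.0 = 0.595. Progression hazards are these minus 0.004, that is 0.0542 and 0.0307. Implied OS medians are about 41.5 and 50.5 months, near the 40 and 50 in Protocol 9.7.2.

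**Step 3: late deaths only** (200,000 per arm). *As written*: any captured death to cutoff is an event. *Symmetric*: a death counts only up to next line or last visit.

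| Scenario (monthly switching, palbociclib + AI / AI) | Late deaths, % of rwPFS events | HR as written | HR symmetric | AI median as written / symmetric (months) |
|---|---|---|---|---|
| No effect, 1% / 1% | 7.6 / 7.6 | 1.000 | 1.001 | 12.2 / 11.9 |
| No effect, 0.5% / 2% | 5.1 / 12.4 | 1.020 | 1.002 | 12.4 / 11.9 |
| No effect, 0.5% / 4% | 5.0 / 21.2 | 1.044 | 1.002 | 12.9 / 11.9 |
| No effect, 2% / 2%, AI indexed earlier | 8.7 / 15.1 | 1.083 | 1.006 | 12.7 / 11.9 |
| 20.0 vs 11.9, 0.5% / 0.5% | 6.4 / 5.1 | 0.608 | 0.597 | 12.1 / 11.9 |
| 20.0 vs 11.9, 0.5% / 4% | 6.5 / 20.9 | 0.625 | 0.594 | 12.9 / 11.9 |

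Under a true effect the shift is 0.608 − 0.597 = 0.011 to 0.625 − 0.594 = 0.031. Across scenarios the median gap from next line or last visit to the counted death was 15-21 months.

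**Step 4: late progressions as well.** In a further set of runs with a true effect, the HR was 0.595-0.597 under symmetric censoring, 0.614-0.619 with late deaths only, and 0.574-0.615 with late progressions too. With no effect and unequal switching it was 1.03 with late deaths only and 0.93 with both. A separate model with assumed rates gave 0.60-0.64 against 0.58-0.60 symmetric, a shift of up to about 0.04; there the palbociclib + AI median fell to 18.5-19.8 months, where counting late deaths alone raised it to 20.3-20.6.

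The sign changes for a plain reason. Late deaths alone add long event-free time to the arm that switches more and lower its apparent hazard. Late progressions add many events, while patients with no later event lose their time after switching, and this raises it.

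**The case against.** **Unseen vendor rules.** The Abstract and the opening of 9.3 refer to the data vendor's rules, which are not in the documents and may already limit countable deaths. That is possible, but neither analysis text says so, and the rule on paper is what would be programmed.

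**The intention-to-treat contrast in Protocol 9.1.** If it extends to rwPFS, deaths after next line may properly count. Then patients without a later event must not be censored at next line either. The text takes one position for them and the other for those who die.

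**The symmetric rule is not free of bias.** This stands. If, by assumption, 15% of progressions go undocumented and prompt the switch, the symmetric rule gave medians of 14.0 and 23.0 months against true values of 12.1 and 20.3, while the rule as written gave 13.3 and 21.4. HRs were 0.606 and 0.609 against a true 0.600. A window for deaths after last contact also leaves some asymmetry.

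**Size.** The shifts are small beside the earlier study's 95% CI of 0.49-0.69. True, but that study's precision does not justify outcome-dependent censoring, and medians and landmark rates move too.

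**Stronger readings.** A reader might infer that the rule favors palbociclib + AI, or always pulls the HR toward 1. Neither is supported: the direction changes with switching rates and with whether late progressions count. Nor can one say that deaths years later are known to be in the data. That is inferred from the missing limit and the linkage, and is bounded by the cutoff (stated as 30 September 2020 in 9.2.1 and SAP 4.1, but 2021 in 9.1). Nor do all deaths come from outside sources; the EHR is one of the three.

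**Conclusion.** The rule is wrong as written for rwPFS and rwPFS2, not merely short of detail, and the four rwPFS texts do not agree. The primary OS analysis is unaffected.

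The logical fault rests on the text alone; the size does not. Over the runs above, the HR shifts by about 0.01 to 0.04 under a true effect. With no effect it stays near 1.00 when the arms behave alike, and ranges from about 0.93 to 1.08 when switching or index dates differ by arm. Medians shift modestly, for example from 11.9 to 12.1-12.9 months for AI alone when only late deaths are counted. These ranges describe the assumed rates and are not bounds; a wider gap in switching between the arms would move the results further. The change should be made before the secondary analyses are run.

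**What to change.** Reconcile the Abstract, Protocol 9.3, Protocol 9.7.4.3 and SAP 5.1 into one rule:

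- Every patient without an earlier event ends rwPFS observation at the earlier of next-line start and last visit (or last clinic note; choose one), whether or not they later die or progress.
- Death is an event only before next-line start and within a short, pre-stated window after last contact. Justify its length and make it workable with death dates that are mostly known to the month. A trial value of 90 days left the HR at 0.596-0.598 against 0.595-0.597 under symmetric censoring, but 90 days has no source in the documents.
- Apply the same rule to rwPFS2 with third-line start as the boundary.

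Add to SAP 7.2, as sensitivity analyses, the current rule and a version that treats next-line start as an event or ignores it, in case switching reflects undocumented progression. Report by arm how many patients start a next line without documented progression, and how many deaths fall after next line or last contact.

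Cost: a few sentences, one programming rule and slightly fewer rwPFS events. The remaining weakness is that the symmetric rule is itself biased if switching reflects undocumented progression; the sensitivity analyses are there to show how much that matters.
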